8.3.3.1. Case Ascertainment and Validation Process

The incidence of AESIs within disease-specific risk windows following the administration of the Ad26.COV2.S vaccine will be ascertained using diagnosis codes that were developed and reported to EMA for the ACCESS study ([ACCESS 2021](#)). Additional and more refined electronic algorithms (e.g., by requiring multiple codes, or having confirmatory medications/procedures, laboratory values or laboratory assessment) will be created and described in the SAP and assessed in the feasibility assessment. It will also be described how to assess the case index date, whether this will be based on a diagnosis or the first retrievable symptom.

For the safety evaluation study, case validation to confirm the disease diagnosis and date of onset may be conducted on AESIs that are judged likely to be misclassified based on clinical expert opinion, prior validation studies (if available), and data access providers. Manual review of medical records or chronological listings of diagnosis, procedure, and pharmacy dispensing codes in patient profiles by clinicians may be conducted, depending on the AESI. Where available, Brighton Collaboration definitions or any other clinical definitions from published literature or learned societies will be used as case definitions if medical record review is implemented for the AESI. For outcomes selected for validation, a sampling strategy will be implemented based on the rarity of events and identified cases in the study population, to identify cases that will undergo case validation. Following case validation, if the positive predictive value (PPV) of a given AESI is above a pre-specified threshold (e.g., $\geq 80\%$), all identified cases in the electronic data will be included in the final analysis. If the PPV is lower than the pre-specified threshold (e.g., $< 80\%$), then the validation results will be used to inform or adjust relative risk estimates (e.g., in quantitative bias analysis) in electronic data. The PPV threshold for determining whether all cases identified in electronic data are to be included in the final analysis will be specific to each AESI and will depend on the background rate of each AESI. The sampling strategy, the selection of which AESIs are to be validated and the rationale for selection, details on the methods for validation, and the plan for integrating the validation results into the final analysis will be described in a data validation plan.

SIDIAP (ES): In SIDIAP, the validation process is part of data quality control. On the other hand, specific validation studies on selected endpoints will be based on the review of the electronic medical record information by the own primary care clinicians exploring the overall coded and text information and existing reports.

VID (ES): In VID, validation will be based on the review of the electronic medical record information by members of the FISABIO research group who will be blinded to COVID-19 vaccination status.

PHARMO DATABASE NETWORK (NL): For validation, information on selected endpoints from patient medical records will be abstracted by local medical professionals or PHARMO

employees, provided that medical record review is approved by ethics committees and other local and/or national governing bodies.

ARS (IT): Review of medical records is not possible for ARS. See section 8.2.1 regarding conditional participation of ARS Toscana

8.3.4. Covariate Definition

Feasibility Assessment

In the feasibility assessment, covariates will be assessed at the time of COVID-19 vaccine administration or time-matched non-vaccinated individuals.

Safety Evaluation Study

Covariate assessment for the description of the patient population at baseline (index date) will use all available time of enrolment in the corresponding data source (minimum required enrolment period is 1 year).

Covariates will be assessed at index date (for the cohort design) to define patient populations of special interest or priority vaccination groups, to define subgroups of interest for sensitivity analyses, or to control for confounding.

We will consider the following time-varying covariates and corresponding period of evaluation for the SCRI measured at start of the risk window and the control window. To capture use of medications of interest during the month prior to start of the study periods (i.e., risk control and control risk), we will consider the drug supply covering the month prior to the start of the two periods of interest.

- Analgesics (month prior)
- Antibiotics (month prior)
- Antiviral medications (month prior)
- Systemic Corticosteroids (month prior)
- Immunosuppressant therapy (month prior)
- Non-steroidal anti-inflammatory drugs (month prior)
- Heparin (month prior)
- Novel oral anticoagulants (month prior)
- Warfarin (month prior)
- Aspirin (month prior)
- Influenza vaccine (month prior)
- Any pneumococcal vaccine (month prior)
- Any herpes zoster vaccine (month prior)

-
- Human papillomavirus vaccine (month prior)
 - Meningitis vaccine (month prior)
 - Pregnancy (at start of each window of interest)
 - COVID-19 infection (month prior)

For the cohort design, covariate status for all time-varying factors will be measured at index date. All covariates will be assessed in specific periods. For the secondary analysis in dedicated subgroups or patients with a past history, any time prior as the look-back period for the assessment of the covariates will be used, reference point is index date. For vaccinations other than COVID-19, follow-up time will be censored in a sensitivity analysis.

Population characteristics will be identified based on diagnoses, medicines, laboratory data, survey observation or medical observations, and observation period information.

Demographic characteristics

- Age
- Sex
- Pregnancy

Pregnancy status and pregnancy trimester at index date.

- Frailty

The eFI frailty score as described by Clegg et al ([Clegg 2016](#)) with a count of the number of different conditions will be created. Details will be available in the SAP.

Comorbidities (any time prior)

- Cancer (other than non-melanoma skin cancer)
- Chronic kidney disease (exclusion for acute kidney injury)
- Acute coronary syndrome (exclusion for cardiac/cardiovascular events)
- Chronic respiratory disease (chronic obstructive pulmonary disease, asthma)
- Obesity
- Down's syndrome
- Type 1 (excluded for type 1 when AESI) or type 2 diabetes
- Prior thrombosis (exclusion for thrombosis as outcome – see [Table 1](#))
- Morbidity index: number of different ATC codes (Level 5) dispensed in the year prior to cohort entry
- History of anaphylaxis
- History of any type of allergic reaction
- Immunocompromised conditions (will be used to define subgroups for secondary analyses)

-
- Immunodeficiencies
 - Systemic Immunosuppressant medication use
 - Human immunodeficiency virus and other immunosuppressing conditions
 - Parkinson’s disease
 - Stroke/brain injury
 - Dementia
 - Difficulty walking
 - Chronic use of home oxygen (>3 months of continuous use)
 - Palliative care
 - Heart failure (exclusion for heart failure as an outcome).

Covid-19 History

- Prior recorded COVID-19 infection as yes/no for the feasibility studies and by severity for the final study (non-hospitalised, hospitalised)

Comedication (dispensed/prescribed/used in period or episode covering this period)

- Analgesics (month prior)
- Antibiotics (month prior)
- Antiviral medications (month prior)
- Systemic Corticosteroids (month prior)
- Non-steroidal anti-inflammatory drugs (month prior)
- Psychotropics (year prior)
- HMG-CoA Reductase Inhibitors (statins) (year prior)
- Novel oral anticoagulants (month prior/time-varying)
- Warfarin (month prior)
- Aspirin (month prior)
- Oral contraceptives (year prior)
- Hormone replacement therapy (year prior)
- Heparin (month prior)
- Immunosuppressants
- Use of antihypertensive drugs.

Vaccinations

- Administration of any other COVID-19 vaccine from the reference date until the end of the follow-up period (censoring criterion)

-
- Influenza vaccine (month prior/time-varying)
 - Any pneumococcal vaccine (month prior/time-varying)
 - Any zoster vaccine (month prior/time-varying)
 - Human papillomavirus vaccine (month prior/time-varying)
 - Meningitis vaccine (month prior/time-varying).

Health Care Utilisation in the Year Before and in the 4 Weeks Prior to Index Date

- Number of individuals with at least one hospitalisation (hospitalisation data sources)
- Number of individuals with at least one GP-visit (Primary care data sources)
- Number of different dispensed/prescribed drugs ATC Level 5 dispensed (all data sources)

The AESI may have different sets of risk factors, and outcome-specific analyses may contain different covariate sets. Potential covariates may include the following information, as available in each data source. For the SCRI design, covariate status will be measured at start of risk window and control window for time-varying factors.

For the secondary analyses in subgroups, the following categories will be used:

- Immunocompromised individuals,
- Pregnant women,
- Prior COVID-19 infection,
- Individuals who have a prior history of thrombotic events or thrombocytopenia,
- Individuals with a prior history (ever) of that event (i.e., more than a year before).

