8.1.2.1. Self-controlled Risk Interval Design (Primary Study Design for Acute Events)

The SCRI design will compare the risk of the AESI in a post-vaccination risk window to a pre-vaccination control window (sensitivity analysis) and post-vaccination control window (main analysis) within the same individual.

The SCRI design will include only individuals in the primary analysis who received at least one first-ever dose of the Ad26.COV2.S vaccine during the study period. Vaccinated individuals enter the study at the date of the start of the pre-vaccination control window. The SCRI design will compare the risk of each outcome during the post-vaccination risk window following the COVID-19 dose with a self-matched control interval that may be prior to vaccination, or after the vaccination risk window, to assess the baseline risk of the outcome. The control window will have the same maximum length as the risk window to minimise time-varying confounding that cannot be measured. In case the follow-up time does not capture the maximum post-vaccination risk or control window due to right censoring, all available follow-up time will be utilized. Follow-up will be censored upon vaccination with another COVID-19 vaccine or end of follow-up. A washout period between the control and risk window will be applied to minimise capturing of prevalent events during the risk window. A post-vaccination control window may induce a bias towards the null when an AESI that was identified during the vaccination risk window, is captured again during the control window due to a re-admission instead of reoccurrence of the AESI. This situation is more likely to be encountered for acute potentially recurring events such as cardiac events (including acute coronary syndrome, myocarditis, pericarditis, arrhythmia, and stress cardiomyopathy). Moreover, due to lag-times in updating the relevant databanks, there is a higher risk that the post-vaccination control window may not capture all events and underestimate the rate of events. Use of a pre-vaccination control window will deal with these issues. In a sensitivity analyses, we will use a pre-vaccination control window and a post-vaccination control window will be used for the main analysis. In a sensitivity analysis, vaccination to other non-COVID-19 vaccines will also be an exclusion and censoring event.

We will also compare the Ad26.COV2.S vaccine with active comparators with 1) only 1-dose strategy and 2) a 2-dose strategy.

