Abbreviations: ADEM = Acute disseminated encephalomyelitis, AESI = adverse event of special interest, All non-acute events are considered to have a washout period of 365 days. * For diabetes mellitus which is a chronic condition we will use any time prior for washout.

Exacerbation of asthma ascertainment will require the definition of an asthma cohort and identifying exacerbations of asthma within that cohort.

The asthma cohort will be defined by having:

- a code for asthma and;
- at least 2 prescriptions for an inhaled corticosteroid within 5 years before the index date.

Among this asthma cohort, an exacerbation of asthma was defined by having:

- At least 1 prescription of a systemic glucocorticosteroid during the defined risk window or;

- At least 1 hospitalisation for asthma during the defined risk window.

The date of this event will be the date of the first prescription of a systemic glucocorticosteroid or the admission date for hospitalisation for asthma, whichever comes first.

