8.7.1.3. Self-controlled Risk Interval Design**Descriptive Statistics**

The number of cases of each AESI will be reported in the control and risk windows, overall and by important covariates.

Measures of Association

Conditional Poisson regression will be used to estimate incidence rate ratios and 95% confidence intervals (CIs). The SCRI inherently adjusts for both measured and unmeasured time-constant factors such as sex and chronic health conditions with onset before the start of follow-up. Time-varying confounders (e.g., medications and other vaccinations) may be included as covariates in regression models. Subgroup analyses will be conducted by groups defined by demographic and clinical characteristics and other covariates of interest.

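### SCRI medication covariates for the post-vaccination control window can record treatment of a risk-window event; a model that includes them for an AESI they treat or define is biased downward

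*Protocol*

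**What the plan says.** Protocol 8.1.2.1 compares the risk window with a "post-vaccination control window (main analysis) within the same individual"; the pre-vaccination control window is a sensitivity analysis, and Table 5 in 8.7 agrees. On length, "The control window will have the same maximum length as the risk window". Section 8.1.3 puts a buffer between the two windows and leaves its length to the SAP.

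Section 8.3.4 lists "time-varying covariates and corresponding period of evaluation for the SCRI measured at start of the risk window and the control window". For medicines, "we will consider the drug supply covering the month prior to the start of the two periods of interest". The list includes heparin, novel oral anticoagulants, warfarin, aspirin, systemic corticosteroids, immunosuppressants, antibiotics, antivirals, analgesics and NSAIDs, together with other vaccines, pregnancy and COVID-19 infection.

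Section 8.7.1.3 states: "Time-varying confounders (e.g., medications and other vaccinations) may be included as covariates in regression models". Section 8.3.4 also says that covariate sets may differ by outcome.

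The acute AESIs in Table 1 include deep vein thrombosis, pulmonary embolism, sinus thrombosis, stroke, coronary disease, immune thrombocytopenia and asthma exacerbation. Section 8.3.3 accepts either of two criteria for an asthma exacerbation: "At least 1 prescription of a systemic glucocorticosteroid during the defined risk window", or a hospitalisation for asthma.

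**The concern.** A covariate used to remove confounding should not be a consequence of the outcome. Here the risk-window value is read before an event in either window. The control-window value is read after a risk-window event could have occurred. If that event is treated with a listed drug, the drug is recorded as present for the control window because of the event. Only risk-window cases can show this pattern.

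The conditional model then reads the drug as protective and estimates the vaccine effect largely from untreated cases. In a safety study the error runs toward hiding harm. In the pre-vaccination sensitivity analysis it runs upward, because treatment of a control-window event can fall in the look-back before the risk window. The two SCRI analyses could then disagree for an artefactual reason.

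The comorbidity list in 8.3.4 already drops items that coincide with the outcome (prior thrombosis, heart failure, acute coronary syndrome). The SCRI drug list has no such exclusion.

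**Working it through.** **Inputs from the protocol.** Equal windows (8.1.2.1); risk windows of 0-2, 1-14, 1-28, 1-42 or 1-60 days (Table 1); one-month look-back (8.3.4); conditional Poisson model (8.7.1.3).

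**Assumptions.** The month is 30 days. Buffer *B* is varied. *t* is the share of risk-window cases whose treatment is recorded in the look-back before the control window. *b* is background use of the drug in each window. The drug has no causal effect on the event. Two-sided alpha is 0.05, which is not stated for the SCRI tables but reproduces them.

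**1. The plan's own figure.** Table 3 gives 92.6% power for 100 events and RR 2. The signed-root likelihood-ratio formula with *r* = 0.5 and β = ln 2 gives:
- *A* = 2[(1/1.5)(0.6931) − ln 1.5] = 2(0.4621 − 0.4055) = 0.1133
- *B'* = (0.6931²/0.1133) × (0.5/1.5²) = 0.943
- Power = Φ[(√(100 × 0.1133) − 1.960)/√0.943] = Φ(1.448) = 92.6%

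This agrees. All rows of Tables 3 and 4 are reproduced, so those tables are sound for an unadjusted comparison.

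**2. Overlap.** For a risk window of *L* days, overlap = min(*L*, max(0, 30 − *B*)). With *L* = 28 and *B* = 0, 7, 14, 21, 28, 30, the overlap is 28, 23, 16, 9, 2, 0 days. From 30 days on there is no calendar overlap, but supply that continues after treatment starts still counts, because 8.3.4 uses supply covering the month. For asthma (*L* = 14), the whole risk window lies in the look-back whenever *B* ≤ 30 − 14 = 16 days. Then *t* = 100% for every prescription-defined risk-window case.

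**3. Bias formula.** With two equal windows the model reduces to P(event in risk window) = expit(β + γ(x_risk − x_control)). As *b* approaches 0, all treated risk-window cases have difference −1 and are fitted by γ. The rest have difference 0 and determine β:

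adjusted RR = RR × (1 − *t*)

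For RR 2 and *t* = 50%, this is 2 × 0.5 = 1.0. In the pre-vaccination analysis the mirror result is RR/(1 − *t*) = 2/0.5 = 4, with *t* now the treated share of control-window cases.

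**4. Larger background use.** Large-sample solutions for a true RR of 2, with background use independent between windows:

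| *b* | *t* = 25% | *t* = 50% | *t* = 70% | *t* = 90% |
|---|---|---|---|---|
| near 0 | 1.50 | 1.00 | 0.60 | 0.20 |
| 5% | 1.73 | 1.24 | 0.78 | 0.33 |
| 10% | 1.82 | 1.41 | 0.97 | 0.48 |
| 20% | 1.90 | 1.62 | 1.28 | 0.82 |

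At *b* = 5% and *t* = 80% the result is 0.55. If background use persists within person (correlation 0.8 assumed), *t* = 20/50/80% gives 1.69/1.09/0.49, against 1.81/1.23/0.55 when independent. With a true RR of 1, *t* = 50% and *b* = 5%, the adjusted RR is 0.60.

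**5. Power.** In 2,000 simulated studies per setting (100 events, true RR 2, *b* = 5%), a significant increase is found in 92, 69, 15, 0.7 and 0% for *t* = 0, 25, 50, 70 and 90%. A falsely significant protective result appears in 16% at *t* = 70% and 88% at *t* = 90%. The unadjusted median RR stays at 2.03 throughout, with power of 92 to 94%.

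**The case against.** The strongest reply is that nothing in the protocol forces this model. Section 8.7.1.3 says covariates may be included, and 8.3.4 lets the set differ by outcome and allows covariates to serve purposes other than confounding control. An SAP that left anticoagulants out of the thrombosis models would comply. That stands. A reader might infer that the primary acute-event result will be erased or reversed as planned; the documents do not support this, because no section makes an adjusted SCRI the main estimate.

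Other stronger readings also fail:
- Overlap is not certain, because the buffer length is left to the SAP.
- A high treated share cannot be assumed for thrombosis or any other AESI. The documents give no figure, and incomplete capture of inpatient drugs (ARS inpatient dispensing is described as partial in 8.4.4) could lower it. Reversal needs most risk-window cases to be recorded with a listed drug; otherwise the bias is attenuation.
- Asthma has a second criterion, hospitalisation, so the covariate coincides with the outcome for prescription-defined cases only.
- The problem does not extend to every listed covariate. Antibiotics and antivirals can stand in for infection, a time-varying risk factor named in 8.9, and the listed vaccines are not treatments for the AESIs.

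The pre-vaccination SCRI and the cohort analysis offer some cross-check. A divergence would show that something differs without identifying this cause.

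What survives is that the timing rule and the drug list are stated in the protocol, and a model adjusted as they allow would be biased.

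**Conclusion.** The point holds as a conditional one. Read as written, 8.3.4 and 8.7.1.3 permit adjustment for a drug whose control-window value can result from a risk-window event, by calendar overlap if the buffer is under about 30 days or by continuing supply if it is longer. Entered for an AESI that it treats or defines, such a drug biases the main SCRI estimate downward and the pre-vaccination estimate upward.

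The size ranges from slight attenuation to reversal, and where a given AESI falls depends on the treated share and background use, both assumed here. The mechanism depends on neither value, only on some risk-window cases being treated. Asthma exacerbation is the clearest case, because there the link comes from the protocol's own outcome definition.

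**What to change.** In 8.3.4 and 8.7.1.3, state that:

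- the main SCRI estimate is unadjusted, or adjusted only for factors the event cannot trigger, such as calendar time and other vaccinations;
- for each AESI, listed drugs that treat or define it are used for description only and stay out of its SCRI model: for example anticoagulants, heparin and aspirin for thrombotic, coronary and stroke AESIs, and systemic corticosteroids and immunosuppressants for immune AESIs and asthma exacerbation;
- drugs that act as proxies for infection (antibiotics, antivirals) may remain for AESIs they do not treat.

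A blanket ban on reading any covariate after an earlier AESI is not advised. It would remove control-window values for risk-window cases and keep them for control-window cases, so measurement would depend on the outcome.

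The cost is wording in the protocol and SAP. The small downside is that genuine short-term changes in the excluded drugs go unadjusted; stable use is already controlled within person. With the drugs left out, the simulated median RR is 2.03 under a true RR of 2, and power matches Table 3.

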The sponsor has created a list of AESIs based on current knowledge of the Ad26.COV2.S vaccine. Background incidence rates for most of the data sources and AESIs are available on the VAC4EU dashboard <https://vac4eu.org/covid-19-tool/>. Definitions and codes are available on Zenodo (<https://zenodo.org/communities/vac4eu/>).

Covariate definition

Feasibility Assessment

In the feasibility assessment, covariates will be assessed at the time of COVID-19 vaccine administration (index date).

Safety Evaluation Study

For the cohort analysis, covariates for the study populations will be defined at the index date. For the SCRI design, time-varying covariates will be identified both at the start of the risk window and the control window.

Covariates will be used to define and describe the study cohorts and populations of special interest and their baseline characteristics and/or to control for confounding. Additional covariates may be added during the conduct of the study if deemed important. The look-back observation period to define covariates of interest will be all available information before the index date in each data source with a minimum of 12 months, except when an alternative look-back window is specified.

Data Sources

The study will use data from secondary electronic health record databases that are population-based. All data sources will have the ability to provide data on COVID-19 vaccines, outcomes (diagnoses, procedures, laboratory results, and treatments), and important covariates. It is not currently known the extent to which COVID-19 vaccines, product types, and batch numbers will be captured in data sources. To be included in the study, data sources should preferably be updated at a minimum once every 3 months. At the proposal stage, members of VAC4EU were offered the option to participate in the study. Four data sources from 3 countries (Spain, the Netherlands and Italy) will be included in the study. A more detailed description will be included in the VAC4EU FAIR Catalogue.

When establishing the agreements with the data sources to conduct the study, it will be emphasized that the current list of AESIs may be expanded during the course of the study to accommodate newly identified AESIs.

Study Size

The study will be conducted in a source population of approximately 18.1 million individuals, although children will not be vaccinated. It is assumed that up to 10% will be vaccinated with the Ad26.COV2.S vaccine.

Main Statistical Methods

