8.7.2. Main Statistical Methods

8.7.2.1. Matching

For the cohort designs, matching will be used to ensure comparability on observed covariates between groups to be compared. There will be a match on the following key variables at index date:

- Age (year of birth)
- Sex
- Pregnancy status
- Immunocompromised state
- Prior COVID-19 infection
- Calendar time (with calliper approach) Prior recorded COVID-19 infection (yes/no)
- Presence of one or more risk factors for severe COVID-19 (e.g., cancer, sickle cell disease, obesity, chronic kidney disease, chronic respiratory disease, human immunodeficiency virus infection).

For the SCRI design, an individual is matched with itself, and therefore analyses will be controlled for all stable variables.

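### The any-time-prior look-back for the immunocompromised subpopulation also covers immunosuppressant drug use, so remote past users count as immunocompromised at vaccination

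*Protocol*

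**What the plan says.** Immunocompromised individuals are one of five secondary subpopulations (protocol sections 7 and 8.7.3). Section 8.3.4 settles how they are found:

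- Its rule for the secondary analyses reads "For the secondary analysis in dedicated subgroups or patients with a past history, any time prior as the look-back period", with the index date as the reference point.
- Under the heading "Comorbidities (any time prior)" it lists "Immunocompromised conditions (will be used to define subgroups for secondary analyses)". The items that follow are immunodeficiencies, "Systemic Immunosuppressant medication use", and HIV with other immunosuppressing conditions. The drug item has no limit on recency or duration.
- The abstract gives the default for covariates: "The look-back observation period to define covariates of interest will be all available information before the index date in each data source", with at least 12 months, unless another window is specified.

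For the same drug class as a time-varying covariate in the self-controlled (SCRI) analysis, section 8.3.4 instead uses "Immunosuppressant therapy (month prior)", based on drug supply covering that month. Section 8.7.2.1 matches the cohorts on "Immunocompromised state" at the index date and gives no definition or window of its own.

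**The concern.** Any time prior suits a condition that lasts. It does not suit a drug whose use may have ended long before vaccination, because the secondary objective concerns people who are immunocompromised when vaccinated. Followed as written, the rule puts current users and remote past users under one label.

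Two things are at stake. First, the subgroup estimate becomes an average over both kinds of user. It then answers the intended question only if the vaccine effect is the same in both. Second, membership depends on how far back a database reaches. The same person could be flagged in a source with long history and not in one with short history, yet section 8.7.1 pools the results across sources.

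**Working it through.** **What the rules select.** Consider a person with one immunosuppressant record well before vaccination, none since, and no immunodeficiency or HIV.

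| Rule | Result for this person |
|---|---|
| Subgroup sentence, 8.3.4 (any time prior) | in the subgroup |
| Comorbidity heading, 8.3.4 (any time prior) | in the subgroup |
| Default look-back, abstract (all available history) | in the subgroup |
| SCRI covariate, 8.3.4 (supply in the month prior) | not exposed |

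The first three rules agree. The fourth shows that the protocol elsewhere treats current supply as the relevant exposure for this class. The missing limit is also not the general style of the list: the morbidity index there is counted over one year, and home oxygen needs more than three months of continuous use. In the cohort comedication list most drugs carry a window, for example "Systemic Corticosteroids (month prior)", but the immunosuppressant entry has none.

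**Dependence on history.** The minimum enrolment is 1 year (8.3.4). SIDIAP holds data since January 2006 (8.4.1), about 15 years before vaccination in 2021. PHARMO follow-up averages 12 years (8.4.3).

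**Illustration of size.** The documents give neither the share of past users nor an IRR by recency of use, so all inputs here are assumed. Let s be the share of flagged people who are truly immunocompromised at index, Rc their IRR and Rp the IRR in the rest, with equal background rates:

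subgroup IRR = s × Rc + (1 − s) × Rp

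With Rc = 3 and Rp = 1 this is 1 + 2s:

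- s = 0.7: 2.4
- s = 0.5: 2.0
- s = 0.3: 1.6

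With Rp = 1.5 and s = 0.5 it is 2.25. With Rp = 3 it stays at 3 for every s.

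**What that means for power.** The plan's Table 4 (8.5.2) was reproduced first, using signed-root likelihood-ratio power for a binomial split p = RR/(1 + RR), two-sided 5%. It gives 80.4% at 29 events for RR 3, 80.9% at 41 for RR 2.5, 80.5% at 69 for RR 2 and 80.3% at 195 for RR 1.5, in line with the table. With Rc = 3 and Rp = 1:

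| s | Subgroup IRR | Events for 80% power (Table 4) | Power at 29 events |
|---|---|---|---|
| 1 | 3.0 | 29 | 80.4% |
| 0.75 | 2.5 | 41 | 65.8% |
| 0.5 | 2.0 | 69 | 44.0% |
| 0.25 | 1.5 | 195 | 18.7% |

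**Does restriction lose more than it gains?** Take 69 SCRI events at s = 0.5. The control window has 23 (11.5 from each half). The risk window has 3 × 11.5 + 1 × 11.5 = 46, so the IRR is 46/23 = 2.0. Keeping only the truly immunocompromised leaves 11.5 + 34.5 = 46 events at IRR 3, above the 29 needed. If instead Rp = Rc, restriction removes events and gains nothing.

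**The case against.** The strongest reply is that the protocol does not apply its heading rigidly. Items in the same list carry their own windows, pregnancy is assessed at the index date although it is also a dedicated subgroup, and the abstract allows exceptions. A missing window for one drug item may be unfinished drafting that the SAP would complete. This explains the gap but does not remove it: no exception is stated for immunosuppressants, and a SAP that required current use would depart from the protocol's explicit subgroup sentence. It could also be said that the nesting of the drug item under the immunocompromised entry is not visible in the text. Its position directly after that entry makes this the natural reading, and the any-time-prior heading covers it either way.

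A reader might infer that matching is degraded in the same way. The documents do not establish that. The any-time-prior sentence covers the secondary analyses, section 8.7.2.1 says only that matching is at the index date, and section 8.3.4 measures time-varying factors in the cohort at index, which can be read as current status. If the wide definition were used, the result would be residual imbalance between current and past users, in an unknown direction. The standardised differences and covariate or propensity adjustment in section 8.7.1.2 would address part of it. In the SCRI each person is their own control, so past users change who is studied and not the internal comparison.

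A reader might also picture a short steroid course long ago setting the flag. Systemic corticosteroids are listed separately from immunosuppressants, so the text does not show this.

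Finally, a one-month window is not the only defensible choice. SIDIAP relies on community pharmacy invoicing (8.4.1) and ARS Toscana's inpatient dispensing is partial (8.4.4), so a narrow window could miss some current users. That stands, and it bears on the length of the window.

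**Conclusion.** The point holds for the drug component of one secondary subpopulation. The stated look-back classes remote past immunosuppressant users as immunocompromised at vaccination, and it makes membership depend on each source's depth of history.

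Bias in the subgroup estimate is conditional. It arises only if the vaccine effect differs between current and remote past users, and it then pulls the estimate towards the effect in past users. The 1 + 2s figures rest on assumed IRRs of 3 and 1, equal background rates and an assumed s. They show what could happen and do not estimate it. It would go too far to say that the estimate is necessarily diluted, or that matched pairs are known to be misclassified. For matching, what is established is that the window is not stated. Separately, immunocompromised state appears in the matching list of section 8.7.2.1 but not in those of the abstract and section 8.1.2.2.

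**What to change.** In section 8.3.4:

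- Keep any time prior for lasting conditions (immunodeficiency, HIV and similar).
- For systemic immunosuppressant use, require recent use at the index date. The rule of drug supply in the month prior, already used for this class in the SCRI, is one option. Another fixed recent window is acceptable if the capture of dispensing requires it.
- Exempt this component from the general any-time-prior sentence.

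In section 8.7.2.1, state that the immunocompromised matching variable uses the same definition, and reconcile that list with the ones in the abstract and section 8.1.2.2.

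The change is to definitions in the protocol and SAP and uses data already extracted. The price is a smaller subgroup with a wider interval, and possible loss of current users whose drugs do not appear in community dispensing.
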